USE OF NORETHINDRONE ACETATE FOR MANAGEMENT OF BLEEDING ASSOCIATED WITH THE ETONOGESTREL CONTRACEPTIVE IMPLANT

[name], [name], [name], [name], [name], [name]

Norton Children's Gynecology, University of Louisville, Louisville, KY

HYPOTHESIS:

Oral progesterone is a useful therapy for the management of bleeding associated with the etonogestrel contraceptive implant.

OBJECTIVE:

The overall objective of this study is to confirm that oral progesterone is an effective way to manage bothersome bleeding; thus increasing the rate of continuation of the etonogestrel contraceptive implant in adolescents.

BACKGROUND AND SIGNIFICANCE:

Of the approximately three million pregnancies annually in the United States, 50 percent are unintended pregnancies. Adolescents bear a significant burden of such unintended pregnancies, with 82 percent of adolescent pregnancies being unplanned (1). It is well documented that adolescent pregnancies have deleterious effects on women's health and educational attainment, the health of newborns, and incur a significant emotional and financial burden, both for the individual and society as a whole. Furthermore, greater than one-third of unintended adolescent pregnancies end in abortion (2).

While most sexually active adolescents report using a method of contraception at some point in their lifetime - they are not typically selecting the most effective methods. Combined oral contraceptives and condoms are the most popular and most requested method of contraception by teenagers (3, 4). Unfortunately, the failure rates of both oral contraceptives and condoms among adolescents are higher compared with all typical users (5, 6). Specifically, adolescent mothers are

documented to have a high rate of repeat pregnancy and are more likely to use ineffective methods and to use effective methods inconsistently or incorrectly (6).

It is encouraging that there has been an increase in the number of adolescents who use long-acting reversible contraceptive (LARC) methods, such as the intrauterine device or contraceptive implant. With 4.5% of adolescents using such methods in 2009, compared to only 1.5% in 2007, and just 0.3% in 2002 (7). In fact, when adolescents were counseled on the full range of contraceptive options and the barrier of cost for LARC methods was removed in a large study, more than two-thirds of females aged 14 – 20 years chose LARC methods (8). It is also promising that national organizations, such as the American Congress of Obstetricians and Gynecologists, have emphasized the importance of LARC method use by adolescents. Specifically, ACOG states that LARC methods are safe and appropriate for most women and adolescents, and that they provide top-tier effectiveness, high rates of satisfaction and continuation (9). Furthermore, the Contraceptive CHOICE project, a large prospective cohort study designed to promote the use of LARC methods to reduce unintended pregnancy, found that sexually active teens using the contraceptive implant or intrauterine device have significantly lower mean annual rates of pregnancy, birth, and abortion (34.0, 19.4, and 9.7 per 1000 teens) compared to sexually experienced U.S. teens (158.5, 94.0, 41.5 per 1000) (10). Data from the contraceptive CHOICE project also demonstrates that teens continued to use LARC methods longer than shorter acting methods (i.e. the oral contraceptive pill and depot medroxyprogesterone acetate injections) – two thirds of teens in the CHOICE project were still using their LARC method at 24 months, as compared with only one third of teens using a non-LARC method (11).

The sub-dermal single rod etonogestrel-only implant offers highly effective, long-acting, reversible contraception (12). It consists of a single rod (4 cm in length, 2 mm in diameter) made of ethylene vinyl acetate, containing 68 mg of etonogestrel that is released subdermally over three years. Prevention of pregnancy is accomplished by several mechanisms – suppression of ovulation, thickening of

cervical mucus inhibiting sperm penetration into the uterus, and alteration of the endometrium. In the clinical trial of 301 Nexplanon (the radiopaque etonogestrel implant) users, no woman became pregnant while the implant was in situ, up to and including 14 days after implant removal. This resulted in an estimated overall Pearl Index of 0.0 (95% CI, 0.0 – 0.56) (12); which translates clinically to >99 percent effective at preventing pregnancy. They are documented to be safe for use in the adolescent population. However, the implant is currently used by less than 1% of U.S. women using contraception, and by 0.5% of those aged 15-19 years (13).

It is well documented that women using the contraceptive implant can expect changes in their menstrual bleeding patterns, and these changes account for the most commonly cited reason for method discontinuation. The bleeding pattern women experience in the first three months after insertion is predictive of future bleeding patterns throughout the duration of use (14). When analyzing 11 clinical trials, bleeding patterns were described as infrequent bleeding in 33.3% of 90-day cycles, amenorrhea in 21.4% of cycles, prolonged bleeding in 16.9% of cycles, and frequent bleeding in 6.1% of cycles (15).

There have been studies that propose management options for treating bothersome bleeding associated with the etonogestrel contraceptive implant – such options include combined oral contraceptive pills, non-steroidal anti-inflammatory agents, mefenamic acid, mifepristone, and doxycycline. Unfortunately there is limited clinical data supporting the effectiveness of these treatments (16-18). To our knowledge, there have been no studies investigating the use of oral progesterone for management of bothersome bleeding associated with the contraceptive implant. Given the success of norethindrone acetate in the management of pain and bleeding in adolescents with endometriosis (19), we chose to use norethindrone acetate as our oral progestin of choice for managing bothersome bleeding associated with the contraceptive implant.

When investigating bleeding patterns, a common challenge encountered is that of patient compliance with menstrual calendars. The burden of keeping a daily menstrual calendar may lead to reduced response rates, incomplete data, and poor data fidelity. The widespread popularity of mobile phone technology has increased the ability to connect with study participants in real time, thus decreasing the reliance on traditional pencil and paper methodology for data collection. There are several potential advantages for using short-message service text messaging (SMS) for data collection: (a) data is time stamped thus providing accurate real-time information, (b) study designers have the ability to ensure data responses conform to a set criteria, (c) automatic SMS texts provide prompts for participants to record the data of interest, (d) data transfer is instantaneous thus reducing data loss or incompleteness, and (e) data collection is more convenient and accessible for participants as they are likely to have their mobile phone devices with them and be familiar with the SMS texting function of their particular device. To our knowledge there have been no studies that use SMS text messaging to record data on daily bleeding patterns – essentially creating a real-time electronic menstrual calendar.

MATERIALS AND METHODS:

We will conduct a prospective study of adolescents using the etonogestrel contraceptive implant. Participants will be recruited from the Norton Children's Gynecology practice in Louisville, Kentucky. This practice provides care to a diverse population of females, from a wide range of socioeconomic statuses, age birth to 25 years.

Inclusion criteria will include any post-menarchal female presenting to the Norton Children's Gynecology practice, who desires to use the etonogestrel contraceptive implant and has access to a mobile phone device.

All patients presenting and choosing to have an implant placed will be offered participation. The study will enroll subjects until 30 active participants are in each study arm; for a total of 60 study participants. In order to achieve the enrollment of

60 active subjects up to 100 participants will be enrolled. All enrollments will be voluntary. Participants will receive compensation for their participation. After obtaining informed consent and assent, participants will provide baseline demographic information, including: age, race/ethnicity, zip code of residence, health insurance provider, number of current and past partners, use of prior contraceptive methods, concomitant condom use, sexually transmitted infection history, age at menarche, menstrual cycle regularity, last menstrual period, weight and height. The date of etonogestrel implant insertion will be confirmed.

All patients using etonogestrel contraceptive implants will receive daily SMS texts in the evening via the Qualtrics SMS program asking them to respond with their bleeding pattern that day. If the SMS text messages are unable to connect to your personal cell phone we request an alternative cell phone number be given in order to reach you. We will record responses according to the World Health Organization definitions of bleeding: (a) bleeding day, (b) spotting day, (c) bleeding-free day [see Table I for WHO bleeding definitions]. At their initial follow-up visit 3 months after Nexplanon insertion, we will identify those who report “bothersome” bleeding patterns. For the purpose of this study, “bothersome” bleeding will be defined as prolonged and/or frequent bleeding, as characterized by World Health Organization-recommended definitions of bleeding. The definitions are listed in Table I.

Bleeding day	Any day with vaginal discharge containing blood that required more than 1 sanitary pad or tampon per day
Spotting day	Any day with vaginal discharge containing blood that required at most one sanitary pad or tampon per day
Bleeding-free day	A day during which neither bleeding nor spotting was reported
Bleeding-spotting episode	One or more consecutive days during which bleeding or spotting was entered in the diary, bounded by bleeding-free days
Amenorrhea	No bleeding or spotting days throughout the 90-day reference period
Infrequent bleeding	Less than three bleeding-spotting episodes in a 90-day reference period, excluding amenorrhea
Normal frequency	Three to five bleeding-spotting episodes in a 90-day reference period
Frequent bleeding	More than five bleeding-spotting episodes in a 90-day reference period
Prolonged bleeding	Any bleeding-spotting episode (uninterrupted) lasting more than 14 days in the 90-day reference period

Table I: WHO bleeding descriptions and patterns

Norethindrone acetate (aygestin) will be used to manage bothersome bleeding. Patients will be prescribed aygestin 5 mg by mouth twice daily for one month, followed by aygestin 5 mg by mouth once daily for two months. Medication will then be discontinued. Patients will be evaluated in the office three months after medication initiation, and then again six months after medication initiation. If the patient is unable to take norethindrone acetate (aygestin) due to medical contraindications or cost, they will receive medroxyprogesterone acetate (provera) 10 mg once daily as alternate oral progesterone. Figure 1 below highlights the study design.

[figure not shown]

Figure 1: Study design

During the aygestin administration, patients will again receive daily SMS texts in the evening via the Qualtrics SMS program asking them to respond with their bleeding pattern that day. We will record responses according to the World Health Organization definitions of bleeding: (a) bleeding day, (b) spotting day, (c) bleeding-free day. Patients not reporting bothersome bleeding after the initial 90 days will continue to record bleeding via SMS texts for the next 6 months to serve as the control group (normal bleeding group).

Participants will be compensated as an incentive to increase daily participation. The participant will receive a pre-paid card if they respond to >70% of text messages over each 90-day cycle and attend the scheduled office visit. Patients will receive a \$5 pre-paid card at visit one (3 months after insertion of etonorgestrel implant), \$10 pre-paid card at visit two (6 months after insertion of etonorgestrel implant), and a \$15 pre-paid card at visit three (9 months after insertion of etonogestrel implant).

At the completion of the study, 9 months after enrollment, participants will receive a SMS text message via Qualtrics with a link to a 12 question follow up survey. The post study questionnaire will assess overall satisfaction with the etonogestrel implant and evaluate participants' perceptions of text messaging as a tool to collect information. See Appendix II.

Participants who have already completed the 9 month study will receive an updated copy of the consent and assent form via mail with a request to sign the updated consent and assent forms. See Appendix III for a copy of a letter to be included with the updated consent and assent. Once the updated consent and assent are received by the investigators at Norton Children's Gynecology the post survey follow up will be sent to the participant by SMS text message via Qualtrics. Study participants who are seen in the office for their 9 month follow up visit will be re-consented in the office.

Patients diagnosed with a sexually transmitted infection during the course of the study will be removed from the study and their data will be excluded from analysis.

All completed demographic data collection forms and electronic menstrual calendars will be kept in a database, de-identified, and stored on a password-protected computer. Study size will be a convenience sample. Based on the current rate of etonogestrel implant insertions in our practice, it is anticipated that 30 participants can be recruited over a six-month period of time.

Data Collection and Analysis

All patients who meet the inclusion criteria and enroll in the study will be sent a text message daily for 90 days (3 months). The daily message will prompt the participant to indicate the bleeding level for the day. This single question will have 4 options:

1. Bleeding Day
2. Spotting Day
3. Bleeding Free Day
4. Prefer not to answer today.

On day 90, descriptive tallies of the responses will be done. Using SPSS v20, an algorithm will count the number of bleeding days, spotting days, and bleeding free days and prefer not to answer (PNA) days; the data record for each participant will contain four count variables (bleeding, spotting, free, PNA). Secondly, the algorithm will identify and tally –according to WHO guidelines in Table 1 - bleeding-spotting episodes (BSE), amenorrhea (AM), infrequent bleeding (IF), normal frequency of bleeding (NF), frequent bleeding (FB), and prolonged bleeding (PB).

Participants who have at least a single episode of FB or PB will be assigned the label of “bothersome bleeding”. Those without a single episode of FB or PB will be labeled “normal bleeding”. Participants in the Bothersome Bleeding group will be offered aygestin to control the bothersome bleeding. Participants in the Normal Bleeding group will continue as before, with no additional medications. Following the principle of intent-to-treat, data from those in the Bothersome Bleeding group will be assigned to the aygestin group, despite that they are not taking it.

During the first month, participants in the Bothersome Bleeding group will take one 5 mg tablets of aygestin twice daily (morning and evening). After 30 days, the dose of aygestin will be halved, such that only one 5 mg tablet is taken daily. Sixty days

later, the Bothersome Bleeding group will discontinue aygestin. Ninety days later, both the normal group and the Bothersome Bleeding group will be re-evaluated.

Data Analysis

A descriptive table will be used to sort participants into Normal Bleeding and Bothersome Bleeding. Non-parametric and parametric statistics will be used to compare the demographics of these two groups.

A **dose-response curve** covering six months will be plotted for the Bothersome Bleeding group to visually reveal the impact of one month of 10 mg of aygestin vs. two months of 5 mg aygestin vs. three months 0 mg of aygestin. Plotted on the curve will be the group averages of the daily bleeding value (1 for no bleeding, .5 for spotting, 0 for bleeding). A second **no-dose curve** will be added to the X-Y plot for the six months of data from the Normal Bleeding group.

Repeated Measure Multivariate Analysis of Variance (RM-ANOVA) with a Between-Subjects variable included, will be conducted (assuming sufficient data is available – e.g., low PNA rates) to compare the first 30 day average bleeding value, the 90 day bleeding average, and the 180 day bleeding average between the two groups.

Planned post-hoc comparisons will evaluate changes between the control group and intervention group at the three time points.

Additional analyses may also include regression analysis to assess for predictive factors related to response to aygestin.

TIMELINE:

October 2014	IRB Submission
November 2014	Anticipated IRB Approval
November 2014 – July 2015	Data Collection
August – September 2015	Data Analysis
October 2015	Submission of preliminary data to the North American Society for Pediatric and Adolescent Gynecology (NASPAG) Annual Clinical and Research Meeting Board
April 2016	Present at the North American Society for Pediatric and Adolescent Gynecology (NASPAG) Annual Clinical and Research Meeting
May 2016	Final manuscript composition and submission for publication

APPENDICES:

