Appendix II:

1	How do you feel about using text messages as a way of telling the researchers about your period or break-through bleeding?	Very happy	Happy	Neutral	Un-happy	Very Un-happy
2	Did you answer the text messages every day?	All of the time	Most of the time	Some of the time	Hardly ever	Never [1]
3	When you were not able to answer the text message, what were the reasons for not doing so? Choose all that apply	Busy doing some-thing else	Forgot about to answer	Lost access to my phone	Ran out of minutes/ texts	Other
4	Did you ever feel annoyed or unhappy about receiving texts from the researchers?	No, never	Rarely	Sometimes	About once a week	Every day
5	Would you be more or less likely to enroll in a future study if that study also used text messages to collect your information?	Much less likely to enroll	Less likely to enroll	Makes No difference	More likely to enroll	Much more likely to enroll
6	Text messages were sent at 6pm every evening. How did you feel about the timing of the texts?		Better earlier in the day	The timing was fine	Better later in the day	
7	For this type of research, another way of collecting data is to have you write your information into a paper-based diary each day. Which method of data collection would you prefer?	Strongly prefer paper-based diary	Prefer paper based diary	Either would be fine	Prefer text-based	Strongly prefer text-based
8	Throughout the study period (up to 270 days), how often did you change your cell phone plan (for example, get a new phone number, change your plan to get more or fewer messages, etc.)?	Never	1 time	2 times	3 times	More than 3 times
9	Did the text message format make it easier or harder for you to give your answer truthfully?	Much Easier	Easier	No difference	Harder	Much Harder
10	How likely do you think your friends would be willing to enroll in a study that uses text messaging for collecting data?	Very likely	Likely	Neither likely nor unlikely	Unlikely	Very unlikely
11	Do you plan to keep your Nexplanon for the next 9 months or longer?	Already removed it	No	Un-decided	Yes	
12	Would you recommend Nexplanon to a friend?	Definitely no	Maybe no	Undecided	Maybe yes	Definitely yes

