Use of Norethindrone Acetate for Management of Bleeding Associated With the Etonogestrel Contraceptive Implant

NCT02353247

Nov. 14, 2016

Data Analysis Plan

The primary hypothesis was analyzed using repeated measures ANOVA (RM-ANOVA) with two groups and three measurements (summary statistics at day-90, day-180, and day-270). To have at least 80% *a-priori* power to detect a medium effect size ($f = 0.25$) at $\alpha = 0.05$, a total sample size of 28 was required with approximately equal sized groups. (G*Power version 3.1.9.2¹; Faul, Erdfelder, Lang, & Bucher, 2007). Anticipating and reacting to high attrition rates, 72 participants were enrolled.

Data cleaning and management was done to identify participants who responded to daily SMS surveys at least 189 times (70% of the 9-month trial). Fifteen (21%) of the 72 participants provided fewer than 100 responses. Another 14 participants (19%) provided between 100 and 188 responses. An additional four participants (9.7%) were removed because they did not respond at least 70% of the days during each 90-day time period. The final data set consisted of 39 participants: 18 in the No Intervention arm and 21 in the Intervention arm. Post-hoc analysis indicated the study was powered at 93%.

¹ NOTE: Faul, F., Erdfelder, E., Lang, A.-G., & Buchner, A. (2007). G*Power 3: A flexible statistical power analysis program for the social, behavioral, and biomedical sciences. *Behavior Research Methods*, 39, 175-191.

Data collection was done with Qualtrics™ (Provo, Utah) and analyses were done using Microsoft Excel (Redmond, Washington) and IBM SPSS Statistics for Macintosh (version 24, Chicago, Illinois).

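### The survey that evaluates text messaging is sent only by text, so poor texters are probably under-represented and acceptability is likely, though not certainly, to be overstated

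*Protocol*

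**What the plan says.** The end-of-study questionnaire has two purposes (Protocol, Materials and Methods). It "will assess overall satisfaction with the etonogestrel implant" and it is to "evaluate participants' perceptions of text messaging as a tool to collect information". It is delivered by text: at nine months "participants will receive a SMS text message via Qualtrics with a link to a 12 question follow up survey". Participants who had finished before the survey was added are mailed new consent and assent forms. Once the signed forms are back, "the post survey follow up will be sent to the participant by SMS text message via Qualtrics".

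Two contacts that do not use texting are already in place, but for consent only: that mailing, and the last office visit, where "Study participants who are seen in the office for their 9 month follow up visit will be re-consented in the office". The only provision for failed texting is a second number: "If the SMS text messages are unable to connect to your personal cell phone we request an alternative cell phone number be given". That is the same channel.

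Several questions in Appendix II concern texting problems. Item 2 asks "Did you answer the text messages every day". Item 3 asks why texts went unanswered, with loss of the phone and an exhausted plan among the choices. Item 4 asks about annoyance, item 7 about preferring a paper diary, and item 8 about changes of number or plan.

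On how well daily texting worked, the SAP reports: "Fifteen (21%) of the 72 participants provided fewer than 100 responses". It goes on to list 14 with 100 to 188 replies and four more who missed 70% in at least one 90-day period. Neither document gives a denominator for the survey, a plan for survey non-response, or a comparison of those who answered it with those who did not.

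**The concern.** The channel being judged is also the only channel through which the judgement is collected. A participant who lost her phone, changed number or stopped answering texts has the experience that items 2, 3, 4, 7 and 8 try to capture, and she is less likely than others to send back an answer. Non-response is then related to the quantity being measured.

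What is at stake is the conclusion about texting as a data-collection tool. The background section of the protocol presents daily bleeding reports by text as something new, so readers may rely on that conclusion when planning other studies. If it rests mainly on people for whom texting worked, it describes them and not all who enrolled.

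**Working it through.** **Counts from the SAP.** The plan has no survey figure to reproduce, so the check starts from the reply counts.

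- Reply rule: 0.70 × 270 = 189 replies.
- Below the rule overall or in a period: 15 + 14 + 4 = 33, and 33/72 = 45.8%.
- Retained: 72 − 33 = 39, which agrees with 18 + 21; 39/72 = 54.2%.
- Fewest replies: 15/72 = 20.8%, each with under 100/270 = 37% of days answered.
- Side note: the SAP prints 9.7% beside the four, but 4/72 = 5.6% (7/72 would be 9.7%). The total of 39 fits four, so this point is unaffected.

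**What can be said without a model.** Suppose only the 39 adequate texters answer and 35 of them (90%) are favourable (an assumption). The share among all 72 could then lie anywhere from 35/72 = 48.6% to (35 + 33)/72 = 94.4%.

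**Two-group illustration.** Let p1 and p2 be the favourable shares among the 39 and the 33, and r1 and r2 their survey response rates. All four are assumptions.

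- True share = (39·p1 + 33·p2)/72
- Observed share = (39·r1·p1 + 33·r2·p2)/(39·r1 + 33·r2)
- Difference = (p1 − p2) × [39·r1/(39·r1 + 33·r2) − 39/72]

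Worked case, p1 = 0.9, p2 = 0.5, r1 = 0.9, r2 = 0.3: observed (31.59 + 4.95)/(35.1 + 9.9) = 36.54/45.0 = 81.2%; true (35.1 + 16.5)/72 = 71.7%; difference +9.5 points.

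| p1 | p2 | r1 | r2 | Observed | True | Difference (points) |
|---|---|---|---|---|---|---|
| 90% | 50% | 90% | 60% | 41.49/54.9 = 75.6% | 71.7% | +3.9 |
| 80% | 40% | 80% | 50% | 31.56/47.7 = 66.2% | 61.7% | +4.5 |
| 90% | 70% | 90% | 30% | 38.52/45.0 = 85.6% | 80.8% | +4.8 |
| 90% | 50% | 90% | 30% | 36.54/45.0 = 81.2% | 71.7% | +9.5 |
| 80% | 40% | 80% | 20% | 27.60/37.8 = 73.0% | 61.7% | +11.3 |
| 90% | 50% | 100% | 0% | 35.1/39 = 90.0% | 71.7% | +18.3 |
| 90% | 30% | 90% | 10% | 32.58/38.4 = 84.8% | 62.5% | +22.3 |
| 90% | 90% | 90% | 30% | 40.5/45.0 = 90.0% | 90.0% | 0 |
| 90% | 50% | 90% | 90% | 46.44/64.8 = 71.7% | 71.7% | 0 |
| 70% | 90% | 90% | 30% | 33.48/45.0 = 74.4% | 79.2% | −4.8 |

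The third formula shows why two conditions are needed: the groups must differ in opinion and also in response. For item 2 the first condition holds almost by definition, because the groups are formed by how often texts were answered. For the attitude items it is plausible but not documented.

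**The case against.** The strongest reply is that the documents contain no survey result at all. A reader might infer from the design that acceptability *was* overstated, by some number of points. That is not supported. Only 72, 39 and 33 come from the SAP; every opinion and response rate above is assumed, and the difference can be zero or negative. This part of the objection stands in full.

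A reader might also treat the 33 as people whom texting failed and whom the survey cannot reach. That goes too far as well. Of the 33, 14 + 4 = 18 sent at least 100 replies, and opening one link is easier than answering 189 or more prompts. The SAP gives no reasons for low counts. Dislike of texts does not stop one arriving, a second number is requested, phone access is an entry criterion, and the items do allow unfavourable answers. So these people are less likely to be counted, but not excluded.

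Nor is the mailed re-consent a filter on texting. It selects on returning mail and applies only to those already finished. The Appendix III letter was not in the text available for this check, so its contents cannot be judged.

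A paper copy has limits too. The pre-paid card goes only to those who answer more than 70% of texts and attend, so poor texters have less incentive to come to the visit. The mailing covers completers only. This stands, and it is why reporting matters as much as the paper copy.

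Finally, a reader might infer that satisfaction with the implant goes unmeasured and that an item on satisfaction with bleeding should be added. Items 11 (intention to keep it) and 12 (recommending it) are indirect but reasonable indicators. A bleeding item would not measure the overall satisfaction that the protocol promises.

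**Conclusion.** The point holds as a cheap improvement to a secondary part of the study. Delivery by text alone is stated for both groups of participants, the fallback uses the same channel, and the group most at risk of being missed is large (33 of 72, with 15 below 100 replies). Following the plan as written would probably tilt the judgement of texting towards those for whom it worked.

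The direction is likely, not certain, and the documents do not allow the size to be estimated. With adequate texters 80–90% favourable, poor texters 40–70% favourable and poor texters answering less often, the illustrations run from about 4 to 18 points. A harsher assumption gives 22, so that range is not a bound. If opinion or response is equal in the two groups, the bias is zero; if poor texters like texting more, it reverses.

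The survey enters neither the hypothesis, the objective nor the SAP's analysis. The repeated-measures comparison of bleeding and its sample size are untouched.

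**What to change.** - Offer the same 12 items on paper at the 9-month visit. Enclose them in the consent mailing to completers, to come back with the signed consent. Keep the text link as an alternative and record the mode of answer.
- Report how many surveys were sent and answered out of all enrolled, broken down by daily reply count (for example under 100, 100 to 188, four with a deficient 90-day period, and the 39 retained). The reply counts are already held for all 72.
- Limit the conclusion on acceptability to the participants represented, because poor texters may also miss the visit.

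Cost: one printed page, a minor amendment, and a mixture of paper and text answers that must be kept in mind when results are pooled. The SAP is dated November 2016 and describes data collection in the past tense. If the survey has closed, only the reporting and the limit on the conclusion still apply.

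### The planned dose-response curve can describe bleeding over time under the regimen, but it cannot support a comparison of 10, 5 and 0 mg, because dose order is fixed and the no-dose line is a different population

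*Protocol*

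**What the plan says.** Protocol, Data Analysis: a dose-response curve "covering six months will be plotted for the Bothersome Bleeding group", and its purpose is "to visually reveal the impact of one month of 10 mg of aygestin vs. two months of 5 mg aygestin", with a third phase off the drug, lasting three months, as the 0 mg level. The plotted quantity is the group average of a daily score: 1 for no bleeding, 0.5 for spotting, 0 for bleeding, so higher is better. A second, no-dose curve "will be added to the X-Y plot for the six months of data from the Normal Bleeding group".

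Protocol, Materials and Methods, gives one regimen for the whole treated group, with both durations counted in months: "Patients will be prescribed aygestin 5 mg by mouth twice daily for one month, followed by aygestin 5 mg by mouth once daily for two". On what follows, it says: "Medication will then be discontinued. Patients will be evaluated in the office three months after medication initiation, and then again six months after medication initiation". The same section provides that those who cannot take norethindrone acetate for medical or cost reasons are switched: "they will receive medroxyprogesterone acetate (provera) 10 mg once daily as alternate oral progesterone".

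Protocol, Data Collection and Analysis: daily texts start at enrolment and run for 90 days before any study drug. A participant with frequent or prolonged bleeding in that window joins the Bothersome Bleeding group; everyone else joins the Normal Bleeding group. All Bothersome Bleeding data are analysed as aygestin data, whether or not the drug is taken.

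SAP, Data Analysis Plan: the primary analysis is a repeated-measures ANOVA with two groups and summaries at days 90, 180 and 270. The SAP does not mention the curve.

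**The concern.** A dose-response curve promises that differences in height along it can be put down to dose. Here the horizontal axis is time. The 10 mg phase is always month 1 of treatment, the 5 mg phase always months 2-3, and the 0 mg phase always months 4-6. Any drift in bleeding with time since insertion, and any effect of one phase lasting into the next, has the same shape as a dose effect.

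The line meant as the zero-dose reference comes from people chosen because they did not have the problem being treated. The protocol's Background section itself says that the pattern in the first three months predicts later patterns, so the two groups have no reason to share a level or a trend. The one stretch of pre-treatment, no-drug data in the treated participants, days 1-90, is left off the plot.

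At stake is what the trial can be cited for. A figure with this title and these labels invites a reader to rank the doses, and the study contains no evidence that can do that without strong assumptions.

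**Working it through.** The documents give no figure for this curve, so there is none to reproduce; the SAP's sample size of 28 and power of 93% concern the ANOVA and do not bear on it. The check is whether a dose contrast can be recovered from what is plotted.

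**Inputs.** Phases after day 90: P1 = 10 mg/day (month 1), P2 = 5 mg/day (months 2-3), P3 = 0 mg (months 4-6). These 1 + 2 + 3 months fill the six-month plot. P0 = days 1-90, recorded but not plotted. The wording of the curve does not date the 0 mg block; the regimen text places it after treatment.

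**1. Treated group alone.** Write the mean score in phase p as T_p = a + t_p + d_p, with time effect t_p and dose effect d_p. Then

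T1 − T2 = (t1 − t2) + (d10 − d5).

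The two brackets never appear apart. In matrix form, an intercept, two period terms and two dose terms make 5 columns of rank 3, and no dose contrast is estimable. Adding the group's own P0 gives 6 columns of rank 4; still none is estimable.

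**2. Adding the Normal Bleeding line.** With N_p = b + u_p,

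(T1 − T2) − (N1 − N2) = (d10 − d5) + [(t1 − t2) − (u1 − u2)].

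The last bracket vanishes only if both groups share one time trend.

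| Model, both groups | Columns | Rank | Dose contrasts estimable |
|---|---|---|---|
| Six months, shared trend, no carry-over | 6 | 6 | all |
| Six months, shared trend, carry-over into the 0 mg months | 7 | 6 | 10 vs 5 only |
| Six months, shared trend, carry-over from month 1 into months 2-3 | 7 | 6 | 10 vs 0 only |
| Six months, group-specific trends | 8 | 6 | none |
| Nine months, shared trend, carry-over into the 0 mg months | 8 | 8 | all |
| Nine months, group-specific trends | 10 | 8 | none |

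Plotting days 1-90 therefore helps only if trends are shared. Selecting the groups on days 1-90 makes a shared trend across day 90 especially doubtful.

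**3. Regression to the mean: where it would appear.** As an illustration only, assume that the groups are formed by cutting a normally distributed bleeding burden so that the worst 21/39 = 0.538 are treated (SAP analysed set). The treated group's mean in the selection period is then φ(c)/0.538 with c = −0.097, that is 0.397/0.538 = 0.737 SD above average. With between-period correlation ρ and no drug effect, the later mean is 0.737ρ and the fall is 0.737(1 − ρ):

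- ρ = 0.3: later mean 0.22, fall 0.52 SD
- ρ = 0.5: later mean 0.37, fall 0.37 SD
- ρ = 0.7: later mean 0.52, fall 0.22 SD

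This fall runs from days 1-90 to what follows. If ρ is the same for every later phase, P1, P2 and P3 all sit at 0.737ρ, and the contribution to differences between the 10, 5 and 0 mg segments is zero. If ρ decays, say from 0.5 to 0.3, later phases look better than earlier ones by 0.37 − 0.22 = 0.15 SD, which would count against the 10 mg segment, not for it.

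**The case against.** The strongest reply is that this is a descriptive figure. The protocol speaks of showing something visually and attaches no test. Inference rests on the ANOVA, and the SAP's version includes day 90, so the treated group's untreated period is in the primary analysis even though it is off the plot. That stands, and it limits the point to the figure and its reading. It does not rescue the dose comparison: if the day-180 summary covers days 91-180, it merges the 10 and 5 mg phases, so the primary model offers no substitute contrast.

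Second, the design is not wholly uninformative. With a shared trend and no carry-over, dose can be recovered from the two lines. The treated group also has its own 0 mg months, and a worsening there would not be explained by regression to the mean. Both statements are correct. But groups formed on the outcome make a shared trend doubtful, and worsening after withdrawal could still reflect time or carry-over and says nothing about 10 versus 5 mg.

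A reader might infer more: that regression to the mean of 0.22 to 0.52 SD would show up on the planned plot as a 10 mg effect. The documents do not support that. The plot starts after the selection period, so the fall is not drawn, and with constant correlation it adds nothing between dose segments. The SD figures also rest on assumed correlations and on selection by a mean score. The protocol selects on episode patterns (more than five episodes, or one longer than 14 days), and 21/39 is the share among retained responders after 33 of 72 were removed, not the share classified at day 90.

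On medroxyprogesterone, the documents give no count, and it may be zero. The daily text asks only about bleeding, and the Appendix I form has no field for drug taken.

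**Conclusion.** The point holds as one about what the figure may be said to show. It can describe bleeding over time under the regimen. It cannot support a comparison of 10, 5 and 0 mg, because dose and time are completely aliased within the treated group, and the second line breaks the aliasing only under a shared time trend and no carry-over. The protocol gives no ground for either assumption, and its outcome-based grouping makes the first doubtful. Participants on medroxyprogesterone, or taking nothing, would be drawn at aygestin doses they did not take; the documents do not say how many.

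The size is a matter of identification, not of SD units: no numerical bias for the planned plot follows from the documents. Nor does the point extend to a claim that the primary ANOVA omits the pre-treatment period.

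**What to change.** - Rename the figure a time-course of bleeding by treatment phase, and state that no dose-effect conclusion will be drawn from it.
- Plot both groups from day 1 to day 270 with the phases marked.
- Label the second line as a different, non-bothersome population instead of a no-dose reference.
- Add a caption saying that the groups were formed on days 1-90, so part of any change at day 90 is expected from regression to the mean without a drug effect. This is needed because the nine-month plot makes that step visible where the six-month plot hides it.
- Where the substitution was recorded, report how many participants took medroxyprogesterone and do not show them under aygestin dose labels. Where it was not recorded, say so.

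The cost is a redrawn figure and a caption, from daily responses the plan already collects. The downside is that the dose comparison claim is given up. No change to treatment is implied.
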